SS will be randomized to one of 3 conditions for a 5-week period: (1) VAR plus a mobile CM intervention, (2) VAR plus a non-contingent reinforcement (NR) control condition, and (3) PLA plus the NR condition. During the first week, participants will undergo a standard 7-day medication (VAR or PLA) dose run-up period and will receive voucher-based reinforcement for texting videos of themselves providing CO samples twice per day, regardless of CO level. In Weeks 2-5, participants will continue to text video samples twice per day and will receive voucher reinforcement that is either contingent upon abstinence, or contingent only upon submitting the video (NR). Participants will visit the laboratory each week to complete assessments of smoking, craving, withdrawal symptoms, mood, subjective effects of smoking and psychiatric symptoms. They will also complete the CPT, cognitive battery, measures of quit interest, and provide a saliva sample for cotinine analysis at the beginning and end of the intervention period. At the end of the intervention, participants will be provided with brief advice to quit smoking and will be offered referrals to community treatments. They will also be administered a debriefing questionnaire in which they are asked to guess their medication condition and asked about the intervention acceptability, their willingness to participate in longer CM trials, and their willingness to receive prize-based incentives rather than vouchers.

Two weeks after Session 6, participants will be contacted by phone and asked about the frequency and quantity of cigarette and other nicotine/tobacco product use since the end of the active treatment period. Those indicating that they have been abstinent in the last 7 days will be provided with taxi transportation and compensation to provide CO verification of abstinence. Participants will be asked whether they have contacted and attended any community cessation treatments, and about their current interest in treatment. Participants will again be offered referrals to cessation treatments in the community. This assessment, including CO verification of abstinence, will be repeated 2 weeks later.

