- Movement disorder measures: Abnormal Involuntary Movements Scale, Simpson-Angus Scale, Barnes Akathisia Rating Scale
- Feasibility outcomes (R33 phase only): median number of sessions attended, percentage of video samples submitted, percentage of those who indicate that they would be willing to participate in a longer CM trial, responses to open-ended questions on the debriefing questionnaire

- Adverse events: Number and type of serious adverse events, adverse event ratings (analyzed individually using one maximum value over the study duration for each person for each expected effect, including the baseline value of each item).

Inclusion/Exclusion Criteria

Inclusion Criteria:

- 1) Men and women
- 2) Ages 18-65
- 3) Have schizophrenia or schizoaffective disorder
- 4) Would like to quit smoking within the next 6 months
- 5) Have smoked at least 10 cigarettes per day in the past year
- 6) Have breath CO level > 10 ppm
- 7) Able to speak, read and comprehend English well enough to complete study procedures

Exclusion Criteria:

- 8) Pregnant, breast-feeding, or unwilling to use medically-approved contraception
- 9) Currently using VAR, bupropion or nicotine replacement therapy for smoking cessation
- 10) Medical disease that would preclude participation in the opinion of the medical monitor
- 11) Unstable psychiatric conditions (hospitalization or change in dose of chronic medication in past 30 days)
- 12) Body mass index (BMI) < 15 or > 38 kg/m²
- 13) Past-month suicidal intention, with or without a specific plan
- 14) Positive urine drug screen or breath alcohol level > 0.01% at screening (one re-test allowed)

Power Calculation and Sample Size

R21 phase:

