A total of 48 randomized participants are planned for the R33 phase. With 20% attrition estimated between enrollment and randomization, we anticipate needing to enroll up to 60 participants (20 per group) to include 48 in the intent-to-treat sample. Given that the PAR-14-230 funding announcement indicates that Stage 1B pilot studies funded through this R33 mechanism “are not expected to have sufficient power to conduct a strong test of efficacy”, we have not attempted to power this study to detect significant differences among the groups. We will focus on determining the feasibility and initial efficacy (i.e., effect sizes) of this intervention to determine if a larger-scale trial is warranted.

Trial Management

List of Participating Sites:

Brown University

Projected Timetable

Recruitment (cumulative)

R21 phase:

Year 1: 24 participants

Year 2: 48 participants

R33 phase:

Year 3: 16 participants

Year 4: 32 participants

Year 5: 48 participants

Target Population Distribution (e.g., women, minorities, etc.)

Age Range: Participants will be 18-65 years of age. Those under 18 will be excluded because the efficacy and safety of VAR in children has not been established.

Gender: Both men and women will be included. About 60% male participants are anticipated because schizophrenia is more prevalent among men (Aleman et al., 2003).

Racial and ethnic groups: Ethnicity/race will not be a selection/exclusion factor for study participation. Based on census data and our recent studies, we anticipate that 75% of participants will be Caucasian, 20% African American or multiracial, 4% Asian, 1% Native American and 15% Hispanic.

Data Management and Analysis

Data Entry, Acquisition and Transmission

Data will be entered directly by the participant or by the Research Assistant. Research materials include paper or computer-administered (Qualtrics or REDCap) questionnaires and tasks, structured clinical interviews, videos of participants providing a breath CO sample, breath samples for analyzing carbon monoxide and alcohol levels, saliva samples for analyzing cotinine, and urine samples for assessing tobacco toxicity biomarkers, illicit drug use and pregnancy.

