Following intent-to-treat principles, all randomized participants will be included in analyses. Baseline characteristics of the groups will be compared using ANOVAs for continuous variables and chi-square tests for categorical variables. CO levels from participants' videos will be averaged to provide a single CO measure for each week. Effects of the treatment groups on dependent measures (CO, total and consecutive abstinent CO samples, cigarettes per day, cotinine, QSU, MNWS, mood, CEQ, Stage of Change, Contemplation Ladder, cognitive scores (baseline co-varied), BPRS, Calgary Scale, AIMS, Simpson-Angus and BARS scores), will be analyzed with generalized linear mixed models (GLMMs) with Group (VAR + CM, VAR + NR, PLA + NR) as the between-subjects factor and Session as the within-subjects factor. We will examine main effects and the Group x Session interaction. This approach controls for correlations from repeated measurements and for person-level covariates. Baseline data will be imputed for missing. Differences will be considered significant when $p \leq .05$ and effect sizes will be calculated (Cohen, 1988). We will examine whether gender and FTND score (≤ 5 vs. ≥ 6) moderate treatment effects by adding these factors (separately) to each model. To examine whether reductions in smoking are mediated by changes in proposed targets, once the Group x Session GLMMs have been conducted, we will add concurrent QSU, MNWS and CEQ Reward and Satisfaction scores as covariates in these models to see the extent to which

smoking outcomes are attenuated by the mediators. We will use the same procedure to explore whether cognitive performance mediates smoking outcomes.

Feasibility outcomes include: median number of sessions attended, percentage of video samples submitted and percentage of those who indicate that they would be willing to participate in a longer CM trial. Responses to open-ended questions on the debriefing questionnaire will be described. Number and type of serious adverse events are expected to be rare so will be reported descriptively. Adverse event ratings will be analyzed individually using one maximum value over the 5 weeks for each person for each expected effect, including the baseline value of each item.

Quality Assurance

Procedures in place to ensure the validity and integrity of the data

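### R33 Aim 3 summarises attendance by a median, which sits at its ceiling and does not identify the proportion retained in VAR + mCM

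*Combined protocol and SAP*

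**What the plan says.** Aim 3 under Aims of the R33 Phase concerns the feasibility and acceptability of VAR + mCM given over several weeks. Power Calculation and Sample Size, R33 phase, explains that the phase is not powered for group differences: "We will focus on determining the feasibility and initial efficacy", in order to judge whether a larger trial is warranted.

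Primary and Secondary Outcome Measures lists, for R33 only, "median number of sessions attended, percentage of video samples submitted", followed by the percentage willing to take part in a longer CM trial and the open-ended debriefing answers. The R33 part of the Data Analysis Plan repeats the list: "Feasibility outcomes include: median number of sessions attended, percentage of video samples submitted". Neither place gives a proportion retained, a split by arm, an interval or a feasibility threshold.

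The only attrition figure for R33 applies before treatment starts: "With 20% attrition estimated between enrollment and randomization".

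The R33 description has weekly laboratory visits and two videos a day. In Week 1 vouchers are paid for videos whatever the CO level. In Weeks 2-5 participants keep sending videos and receive "voucher reinforcement that is either contingent upon abstinence, or contingent only upon submitting the video (NR").

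**The concern.** A count of sessions has a fixed maximum, and in a five-week study many participants may reach it. Once just over half of an arm attends everything, the median equals that maximum and no longer responds to what happens to the others. Yet how many people stay is what a larger trial needs to know about a multi-week intervention.

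The other listed measures only partly fill the gap. The video percentage falls when people leave, but also when people who are still taking part do not send. In VAR + mCM in Weeks 2-5 a video showing smoking earns no voucher, so some participants who smoke may stop sending. Willingness to join a longer trial is asked on a questionnaire given at the end of the intervention, so on that schedule those who left early would not be asked.

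At stake is the reading of Aim 3: a report of median 6 of 6 sessions could accompany full retention or the loss of nearly half the arm.

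**Working it through.** **Inputs**
- Randomized: "A total of 48 randomized participants are planned for the R33 phase".
- Arms and duration: "SS will be randomized to one of 3 conditions for a 5-week period".
- Enrolment: "we anticipate needing to enroll up to 60 participants (20 per group) to include 48 in the intent-to-treat sample".
- Sessions: six, inferred from weekly visits over five weeks and a follow-up call timed from Session 6.
- Videos: 2 per day × 35 days = 70 per person, of which 14 fall in Week 1 and 56 in Weeks 2-5.

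**The plan's own figure.** 48 / (1 − 0.20) = 60 enrolled, as stated, or 20 per group. Equal allocation then gives 48/3 = 16 randomized per arm. The plan does not state the 16.

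**Median by number lost.** With 16 people the median is the mean of the 8th and 9th ordered values. Assume that those retained attend all six sessions.

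| Lost, of 16 | Median if the lost attended 1 session | Median if the lost attended 5 |
|---|---|---|
| 0 | 6 | 6 |
| 7 (43.75%) | 6 | 6 |
| 8 (50%) | 3.5 | 5.5 |
| 9 (56.25%) | 1 | 5 |

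So the median stays at 6 with up to 7 of 16 lost. This is an upper bound. With 7 lost and one of the nine stayers missing a single visit, the 8th and 9th values are 5 and 6 and the median is 5.5.

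If the median were pooled over all 48, it would stay at 6 with up to 23 lost (23/48 = 47.9%). That leaves room for all 16 in VAR + mCM to be lost.

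**How often this would happen.** Treat completion as independent between people, with completers attending everything. The arm median is then 6 when at least 9 of 16 complete.

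| True completion | P(median = 6), 16 per arm |
|---|---|
| 60% | 0.72 |
| 70% | 0.93 |
| 80% | 0.99 |

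**What a retention proportion would show.** Exact (Clopper-Pearson) 95% limits are the 2.5% point of Beta(x, n − x + 1) and the 97.5% point of Beta(x + 1, n − x), with n = 16.
- 9/16 = 56%: 30% to 80%
- 13/16 = 81%: 54% to 96%
- 16/16 = 100%: 79% to 100%

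Under the assumption above, the median is 6 in all three cases.

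**What the video percentage shows.** If 7 of 16 leave on day d, the most that can be submitted is (9 × 70 + 7 × 2d) / (16 × 70).

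| Day of leaving | Maximum submitted |
|---|---|
| 0 | 56% |
| 7 | 65% |
| 14 | 74% |
| 21 | 82.5% |
| 28 | 91% |

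A very high percentage therefore rules out heavy early loss. A median of 6 with 91% submitted still fits anything from 0 to 7 people leaving before Session 6.

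**Smoking without dropout.** Suppose nobody leaves VAR + mCM, every Week 1 video is sent, and half of the Weeks 2-5 samples are abstinent (an assumption; the plan gives no rate).
- No non-abstinent sample sent: (14 + 28) / 70 = 60%
- Half of them sent: (14 + 28 + 14) / 70 = 80%
- All of them sent: 70 / 70 = 100%

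Only the first extreme falls in the 56% to 65% range produced by early dropout.

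**The case against.** The plan has every participant continue sending videos in Weeks 2-5; only the voucher rule differs by arm. A video showing smoking counts as submitted, and the analysis plan expects such videos, because it averages CO over each week and separately counts abstinent samples. A reader might infer that the video percentage cannot tell dropout from smoking. The documents do not support that: it requires participants who smoke to withhold nearly all their non-abstinent samples, which is nowhere described. What stands is narrower: a missing video has no reason attached, and in one arm in Weeks 2-5 smoking is a plausible reason.

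A reader might also infer that the listed measures cannot show whether people stay, or that the plan ignores retention. Both go too far. The median falls once half the arm is lost, and the video percentage limits early loss. A report of median 6 of 6 beside 56% to 65% of videos would itself raise a question. Retention is reviewed at study-team meetings (Frequency of DSM reviews), and the DSMB reviews retention and drop-outs with their reasons. The list in the Data Analysis Plan is worded so that it need not be complete, and I have not seen the text under Content of DSM report. These points stand, but they describe trial monitoring; none makes retention an Aim 3 outcome.

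Finally, no passage ties the decision on a larger trial to the median or to any threshold, and a retention count could be added when reporting. That lowers the stakes. It also shows how little the change would cost.

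**Conclusion.** The point holds in a limited form. The attendance statistic named for Aim 3 is bound by its ceiling and does not identify the proportion retained in VAR + mCM. At its widest, one reported value (6 of 6) covers everything from 9/16 to 16/16 retained, results with exact intervals of 30% to 80% and 79% to 100%. That range rests on three assumptions: 16 per arm, reporting by arm, and no missed visit among those retained. The 44% loss is therefore a maximum, not an expectation. The number of sessions, also inferred, changes the ceiling but not the 44%. The video percentage helps with early loss and leaves the cause of a missing video open. Label: cheap improvement.

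**What to change.** In Primary and Secondary Outcome Measures and in the R33 part of the Data Analysis Plan:

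1. Make the main attendance measure the number and percentage of randomized participants attending Session 6, by arm, with an exact 95% CI. The median may stay as a supplement.
2. Report video submission separately for Week 1, when videos are paid regardless of CO in all arms and submission reflects use of the procedure more cleanly, and for Weeks 2-5. Use all scheduled videos for randomized participants as the denominator in both.
3. Count videos missing after withdrawal separately from those missing before it, and state how the withdrawal date is set.

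The cost is wording in two places. Session attendance and video receipt are already recorded, and drop-outs with reasons are already reviewed in monitoring. The downsides are that the feasibility figure may look less favourable than a median, and that the interval will be wide at 16 per arm.

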cognitive measure scores (with baseline scores covaried), CPT demand indices and within-session changes (post- minus pre-smoking) in CO level and positive and negative mood scale scores. Significant interactions will be followed by simple effects tests. Those who opt not to smoke in Session 8 will not be included in the Group x Abstinence analyses of CEQ, or pre-to-post smoking changes in CO or mood, but will be included in all other analyses (only one SS opted not to smoke in Session 8 in our previous study, Tidey et al., 2014). Latency to relapse will be defined as hours between the start of Session 8 and time of relapse, collected in person at Friday's session and by videoed CO sample in the follow-up week. We will follow up for one week after Friday's session, which is 8 days after Session 8. Thus, the maximum latency until second lapse will be 192 h, at which point data will be censored. Lapse latencies will be compared in VAR vs. PLA using a t-test. We will examine whether gender and FTND score (≤ 5 vs. ≥ 6) moderate the effects of VAR by adding these factors (separately) to each model.

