
- 4) Nicotine Withdrawal: Participants may experience some discomfort when abstaining from smoking. Symptoms can include irritability, frustration, anxiety, depressed mood or sadness, desire or craving to smoke, difficulty concentrating, and increased appetite or hunger. These feelings can be uncomfortable but they are normal, temporary, and usually mild.
- 5) Effects of Varenicline (VAR): The results of the largest study to date of varenicline's efficacy and safety in smokers with and without psychiatric disorders found no increase in neuropsychiatric adverse events attributable to varenicline relative to nicotine patch or placebo (Anthenellie et al., 2016). The most frequent adverse event associated with varenicline is mild to moderate nausea, occurring in 25-45% of users, diminishing over time, and not leading to varenicline discontinuation (Anthenelli et al., 2016; Cahill et al., 2009; Ebbert et al., 2010; Evins et al., 2014; Leung et al., 2011). Other common adverse events include insomnia, abnormal dreams and headaches; serious adverse events have been rare in randomized, controlled phase III studies, and there have been no treatment-related deaths and no known contraindications (Anthenelli et al., 2016; Aubin et al., 2014; Evins et al., 2014). Nevertheless, patients receiving VAR should and will be monitored in this study for changes in psychiatric symptoms including mood and suicidality. Co-Investigators [name], a licensed clinical psychologist, and [name], an addictions psychiatrist, will assess and assist with any participants who experience increases in psychiatric symptoms during the study. We will ask participants to sign a medical release form that will allow us to inform their psychiatrist or other healthcare provider that they are participating in a research study in which they may be receiving VAR under double-blind conditions.

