- 6) Changes in Psychiatric Symptoms Secondary to Changes in Smoking Behavior. Changes in smoking can affect how well some psychiatric medications work due to changes in CYP1A2 enzyme activity. We believe the risks of these events are low given the low incidence of such changes in clinical trials, including a trial that included over 4000 smokers with psychiatric disorders (Anthenelli et al., 2016; Evins et al., 2014). However, we will inform participants about these risks and ask participants to provide us with written permission to notify their treating clinician that they are in a study in which they may receive VAR and a behavioral treatment (R33 phase only) that may affect their smoking rate. Adverse events will be collected weekly using a checklist and open-ended questions. In addition, psychiatric symptoms will be assessed with the BPRS and Calgary Scale at every in-person session and movement disorders will be assessed with the AIMS, Simpson-Angus Scale and BARS at the screening and last session. Moderate-to-severe increases in symptoms (e.g., change from mild/moderate category to severe) will trigger review by [name] or [name], who will meet with the participant if needed. Serious adverse events and unexpected related adverse events will be reported to the Brown University IRB as noted above (see **Regulatory Issues** section). Participants will be given contact information so that they can reach the PI, [name], [name], or study staff at any time to report adverse events. Participants reporting suicidal intention at any time (score ≥ 4 on the Columbia Suicide Severity Rating Scale, suicide plan endorsed on the Calgary Depression Scale for Schizophrenia, or spontaneous reports) will be put in contact with [name] or [name] immediately. The clinician will speak with the participant in person if suicidality is reported during a study visit or by phone if it is reported by phone. The clinicians will then determine the next steps to be taken. Having 2 clinicians on this study increases the likelihood that at least one will be available. However, if neither is available, other qualified clinicians at our research center will speak with the participant. The PI will follow any steps recommended by the clinician (i.e., to continue or discontinue participation).

Potential benefits of participation

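### The adverse-event score, read directly, takes its maximum over the baseline rating as well, which dilutes the drug-placebo difference in checklist symptoms toward no difference

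*Combined protocol and SAP*

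**What the plan says.** The rule appears twice in the combined protocol and SAP.

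- Data Analysis Plan, R33 phase: the ratings are analysed item by item, using "one maximum value over the 5 weeks for each person for each expected effect, including the baseline value of each item".
- Primary and Secondary Outcome Measures, adverse-event entry: "one maximum value over the study duration for each person for each expected effect, including the baseline value of each item". This entry is not limited to one phase, so it also covers R21, whose own analysis section does not mention adverse-event ratings.

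Neither place names a model or test for these ratings, defines a treatment-emergent event, or describes a change-from-baseline summary. Serious events are to be reported descriptively.

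On collection, the Trial Safety section says: "Adverse events will be collected weekly using a checklist and open-ended questions". The same section names the drug's most frequent adverse event as "mild to moderate nausea, occurring in 25-45% of users", and lists insomnia, abnormal dreams and headache among the other common ones.

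**The concern.** Study drug cannot have caused a rating taken before the first dose. If that rating is one of the values in the maximum, it sets a floor under the person's score. Someone who starts with a mild headache and has a mild headache on drug scores the same as someone whose headache went away. Randomisation makes the floor equal on average in the two arms, so it pulls the arm scores together. In a safety comparison, that is the unhelpful direction of error.

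This sentence is the only stated analysis of the checklist ratings as such. For nausea, headache and abnormal dreams, the plan describes no other comparison between arms.

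**Working it through.** **Which reading the text supports.** Where the plan intends covariate adjustment, it says so: "cognitive measure scores (with baseline scores covaried" in the R21 analysis section, and "cognitive scores (baseline co-varied" in the same R33 section as the adverse-event rule. The adverse-event sentence uses neither form. Its direct sense is that baseline is one of the values over which the maximum is taken. The covariate sense remains possible, and under it there is no dilution.

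**The plan's own figures.** It gives no rate, power or sample size for this analysis, so there is nothing to reproduce. The nearest R33 arithmetic is sound: "A total of 48 randomized participants are planned for the R33 phase" and "With 20% attrition estimated between enrollment and randomization" give 48 / (1 - 0.20) = 60 enrolled, as stated. With three equal groups (assumed), R33 has 48 / 3 = 16 per group, or 32 v 16 when the two varenicline groups are pooled. R21 has 48 / 2 = 24 per group.

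**Any-occurrence summary (closed form).** Let b be the baseline prevalence and p the on-study probability, assumed independent. Then

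P(maximum above zero, baseline included) = 1 - (1 - b)(1 - p),

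and the arm difference is (1 - b)(p_VAR - p_PLA). The number of weekly ratings does not enter the factor (1 - b).

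Example for nausea: p_VAR = 35% (inside the plan's range), with p_PLA = 10% and b = 30% assumed.

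- Baseline left out: 35% - 10% = 25 points.
- Baseline included: varenicline 1 - 0.70 × 0.65 = 54.5%; placebo 1 - 0.70 × 0.90 = 37.0%; difference 17.5 points = 0.70 × 25.
- Power, 32 v 16, two-sided 5%: 45% falls to 20%.

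For the same rates, the difference is 22.5 points at b = 10% and 12.5 points at b = 50%.

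**Mean of 0-3 ratings (simulation).** Assumptions: latent normal scores cut at 0.5, 1.2 and 1.9, so that P(Z > 0.5) = 31% have the symptom at baseline; within-person correlation .3-.5; the drug shifts every on-study rating by 0.6-0.8 SD. The rule as written is compared with the post-randomisation maximum adjusted for baseline. Weekly collection gives five on-study ratings over the R33 intervention and, taking one per week of the three-week R21 medication period, three in R21.

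| Setting | Shrinkage of mean difference | Power at 0.6 SD, as written | Power at 0.6 SD, with fix |
|---|---|---|---|
| R33, five ratings, 16 v 32 pooled | about 8-10% | about 48-58% | about 62-68% |
| R21-like, three ratings, 24 v 24 | about 12-14% | about 44-49% | about 64-65% |

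Varying b from 5% to 50% (five ratings, 16 v 32, 0.7 SD shift, correlation 0.3 and 0.6) gives a shrinkage of about 4-12%. At b = 30% and correlation 0.3, for example, the mean difference is 0.742 with baseline included and 0.817 without: 1 - 0.742/0.817 = 9%. With no drug effect, the false-positive rate stays at about 4-6% under either definition.

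**The case against.** The strongest reply has four parts.

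1. *The authors may have meant baseline as a covariate.* This is possible, and it stands as a reason to treat the wording as ambiguous. It does not remove the need to change it: an analyst following the sentence literally would put baseline in the maximum, and the plan uses a different term when it wants adjustment.

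2. *The effect is modest.* This stands for mean ratings: baseline is one of six values in R33. A reader might infer a loss of 20-25%, but that arises only with a single on-study rating per person and 24 per arm, which does not fit weekly collection. The collection section also speaks of assessment at every visit; if every visit were rated, the dilution of the mean in R21 would be smaller still. For an any-occurrence summary the loss does not fall with more ratings.

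3. *Other scales cover the symptoms.* This stands in part. A reader might infer that the rule governs the only comparison of non-serious harms between arms. It does not: withdrawal symptoms, including insomnia, are measured by the MNWS; mood, depression and psychiatric symptoms have their own scales; and these are compared between groups in R33 (in R21, for MNWS negative affect and the psychiatric scores). Marked symptom increases also trigger individual review. None of this gives an arm comparison of nausea, headache or abnormal dreams.

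4. *R33 is expressly not powered for group differences.* This stands against an argument from lost power. It does not excuse bias in effect sizes, which are what the plan says R33 will report.

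**Conclusion.** The point holds as a moderate defect of definition. On its direct reading, the rule dilutes the drug-placebo difference in checklist ratings toward no difference. A reader might infer that it hides treatment-emergent effects altogether. The text does not support that: any worsening above a person's own baseline still raises the maximum, and only on-drug symptoms at or below the baseline rating are lost.

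The dilution of mean ratings is about a tenth in R33 and slightly more in R21. For a yes/no summary it equals the baseline prevalence if baseline and on-study symptoms are independent, so it is small for symptoms that are rare before treatment and substantial for common ones. The rating scale, baseline prevalence, placebo rate, correlation, drug effect and pooling of the varenicline groups are all assumptions; the documents give none of them. In R33 the harm is mainly to the effect sizes reported. If covariate adjustment was intended, the defect is one of wording alone.

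**What to change.** In both the adverse-event entry of the outcome list and the R33 analysis section:

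- define the score for each item as the maximum over post-randomisation ratings only;
- enter the item's baseline rating as a covariate or, as an alternative, report worsening above the person's own baseline;
- name the model, and state in the R21 analysis section that the same rule applies there.

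The same data are used and no visit or measure is added. The cost is wording only.
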